**Table 3 Adverse Event Severity Grading Scale for IRRs and Other Events Not Specifically Listed in NCI CTCAE**

Grade	Severity
1	Mild; asymptomatic or mild symptoms; clinical or diagnostic observations only; or intervention not indicated
2	Moderate; minimal, local, or non-invasive intervention indicated; or limiting age-appropriate instrumental activities of daily living a
3	Severe or medically significant, but not immediately life-threatening; hospitalization or prolongation of hospitalization indicated; disabling; or limiting self-care activities of daily living b,c
4	Life-threatening consequences or urgent intervention indicated d
5	Death related to adverse event d

NCI CTCAE = National Cancer Institute Common Terminology Criteria for Adverse Events.

Note: Based on the most recent version of NCI CTCAE (v4.0), which can be found at: [http://ctep.cancer.gov/protocolDevelopment/electronic\\_applications/ctc.htm](http://ctep.cancer.gov/protocolDevelopment/electronic_applications/ctc.htm)

- a Instrumental activities of daily living refer to preparing meals, shopping for groceries or clothes, using the telephone, managing money, etc.
- b Examples of self-care activities of daily living include bathing, dressing and undressing, feeding oneself, using the toilet, and taking medications, as performed by patients who are not bedridden.
- c If an event is assessed as a "significant medical event," it must be reported as a serious adverse event (see Section 5.4.2 for reporting instructions), per the definition of serious adverse event in Section 5.2.2.
- d Grade 4 and 5 events must be reported as serious adverse events (see Section 5.4.2 for reporting instructions), per the definition of serious adverse event in Section 5.2.2

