### **5.3.5.10 Lack of Efficacy or Worsening of Relapsing Remitting Multiple Sclerosis**

Events that are clearly consistent with the expected pattern of progression of the underlying disease, such as MS relapses or disability worsening should not be recorded as adverse events. These data will be captured as efficacy assessment data only. In most cases, the expected pattern of progression will be based on EDSS score. In rare cases, the determination of clinical progression will be based on symptomatic deterioration. However, every effort should be made to document progression through use of objective criteria. If there is any uncertainty as to whether an event is due to disease progression, it should be reported as an adverse event.

Occasional isolated symptoms that according to the investigator are caused by MS, but do not constitute a full MS relapse, should be reported as an AE, with the causality "Disease under study" (see Section 5.3.4).

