### **5.3.5.11 Hospitalization or Prolonged Hospitalization**

Any adverse event that results in hospitalization (i.e., in-patient admission to a hospital) or prolonged hospitalization should be documented and reported as a serious adverse event (per the definition of serious adverse event in Section 5.2.2), except as outlined below.

The following hospitalization scenarios are not considered to be adverse events:

- Hospitalization for respite care
- Hospitalization for a preexisting condition, provided that all of the following criteria are met:
  - The hospitalization was planned prior to the study or was scheduled during the study when elective surgery became necessary because of the expected normal progression of the disease
  - The patient has not experienced an adverse event

The following hospitalization scenarios are not considered to be serious adverse events, but should be reported as adverse events instead:

- Hospitalization that was necessary because of patient requirement for outpatient care outside of normal outpatient clinic operating hours.
- Elective hospitalizations or surgical procedures that are a result of a patient's pre-existing condition(s) that have not worsened since receiving trial medication. Examples may include, but are not limited to, cholecystectomy for gallstones, and diagnostic testing. Such events should still be recorded as medical procedures in the "Surgeries and therapies" eCRF.
- Hospitalization to receive trial medication such as infusions of ocrelizumab unless this is prolonged (more than 24 hours).
- Hospitalization following an MS relapse as long as the reason for hospitalization is to receive standard treatment with i.v. methylprednisolone.

For a list of serious ADRs that are considered expected, kindly refer to the current IB.

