 - If the date is completely missing, it is considered treatment-emergent
- If the end date is incomplete:
 - If the day is missing, impute to the last day of the month
 - If the day and month are missing, impute to 31DEC
 - If the date is completely missing, it is considered treatment emergent

Serious Adverse events (SAEs): all SAEs including serious MS relapses and serious Infusion Related Reactions (IRRs).

Dose assigned to an AE: only applicable if the AE onset date is on or after the date of the first infusion of that dose but before the first infusion of the next treatment dose. AEs that are reported during the safety follow-up period will be assigned to the last dose received. AEs that start prior to the first dose and worsen during treatment (i.e., treatment-emergent) will be assigned to the first treatment dose.

Output Conventions

All analyses of AE data will be performed using the PTs unless otherwise specified.

For all summary tables, the AEs will be sorted by SOC (in decreasing order of overall incidence) and then by PT (in decreasing order of overall incidence). All summaries and listings of AEs will be based on the ITT population. Summaries of AEs will be generated to summarize the incidence of treatment-emergent AEs only (TEAE and AE are used exchangeable).

A listing of all AEs will be provided, including all relevant information (including -but not limited to- start date, end date and the corresponding study days, related to treatment, seriousness, Grade, treatment-emergence).

Incidence Analysis on number of the events and number of patients with at least one event:

Overview of TEAE, including

- AE
- Serious AE
- Death
- AE with fatal outcome
- Infusion related reaction (IRR)
- Serious infusion related reaction (IRR)
- Infections (using the MedDRA SOC of “Infections and Infestations.”)
- Serious infection (using the MedDRA SOC of “Infections and Infestations.”)
- AE leading to study drug discontinuation (“Drug Withdrawn” for the “Action taken with ocrelizumab due to SAE/AE” field in the “Adverse Event/IRR/MS Relapse” eCRF form)
- Serious AE leading to study drug discontinuation (“Drug Withdrawn” for the “Action taken with ocrelizumab due to SAE/AE” field in the “Adverse Event/IRR/MS Relapse” eCRF form)
- AE leading to dose modification/interruption
- Serious AE leading to dose modification/interruption

- AE related to study medication,
- AE of Grade ≥ 3

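### The protocol gives conflicting rules on whether an MS relapse admitted for steroids is an adverse event, and the SAP does not say whether relapse records enter its AE tables

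*Protocol*

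**What the plan says.** Three places bear on how a relapse is recorded, and all are in current text.

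- **Protocol 5.3.5.10** says that events clearly fitting the expected course of the disease, "such as MS relapses or disability worsening should not be recorded as adverse events", and adds: "These data will be captured as efficacy assessment data only". The general AE definition in Protocol 5.2.1 makes an exception for worsening of an existing disease by pointing to 5.3.5.10 alone.
- **Protocol 5.3.5.11** opens a list with "The following hospitalization scenarios are not considered to be serious adverse events, but should be reported as adverse events instead". One item is "Hospitalization following an MS relapse as long as the reason for hospitalization is to receive standard treatment with i.v. methylprednisolone".
- **SAP 4.6.2** defines serious adverse events as "all SAEs including serious MS relapses and serious Infusion Related Reactions (IRRs").

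Protocol 4.5.4 sends relapses to a dedicated relapse page of the eCRF. SAP 4.6.2, however, reads seriousness, grade, relatedness and action taken from a form whose name combines adverse event, IRR and MS relapse. SAP 4.6.2.1 states how IRRs are picked out (a flag on the AE page) and how infections are picked out (by system organ class). It has no matching rule for relapses.

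**The concern.** A site that follows 5.3.5.10 records no AE for a relapse. A site that follows 5.3.5.11 records a non-serious AE for the same relapse if the patient is admitted for standard steroid treatment, and none if that treatment is given to an outpatient. AE status then depends on local admission practice and on which section the site reads.

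The rate and nature of adverse events are the safety endpoint, and the trial has a single arm. There is no concurrent control in which the same recording habit would appear and cancel out. The outputs most exposed are the overall and non-serious TEAE counts, including the SAP table of non-serious TEAEs in at least 5% of patients, which is produced for the public registries.

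**Working it through.** **Can the rules be read together?**

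| Relapse | Protocol 5.3.5.10 | Protocol 5.3.5.11 | SAP 4.6.2 |
|---|---|---|---|
| Outpatient steroid treatment | Not an AE | Silent | Not stated |
| Admitted only for standard i.v. methylprednisolone | Not an AE | Non-serious AE | Not stated |
| Admitted for another reason, or meets another seriousness criterion | Not an AE if clearly a relapse | General rule: an AE leading to admission is an SAE | In the SAE set |

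The second row is a direct conflict. The third is a gap: the SAP expects serious relapses among the SAEs, while 5.3.5.10 gives no route onto the AE form for a clear relapse. SAP section 4 says that its analyses supersede those in the protocol, but that governs analysis and does not tell sites what to record.

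**Scale, for illustration only.** The plan states no figure to reproduce. The documents give neither an absolute relapse rate on ocrelizumab (Protocol 1.2 has only relative reductions) nor the share of relapses admitted, so both are assumed over a range.

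- Person-years with full follow-up in the treatment period: 750 × 96 × 7 / 365.25 = 1,380.
- Relapses at an assumed ARR of 0.05, 0.10 or 0.20: about 69, 138 or 276.
- Records that change status = relapses × share admitted, with the share assumed at 10% to 60%:

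| Assumed ARR | 10% admitted | 60% admitted | Per 100 patient-years |
|---|---|---|---|
| 0.05 | 7 | 41 | 0.5 to 3 |
| 0.10 | 14 | 83 | 1 to 6 |
| 0.20 | 28 | 166 | 2 to 12 |

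Under 5.3.5.10 each of these counts is zero. They are records, so they are upper bounds on patients.

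**Registry table.** The cut-off is 0.05 × 750 = 37.5, so 38 patients. The range of 7 to 166 spans it. Whether relapse appears in that table can therefore depend on which section sites followed.

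**Proportion with any TEAE.** Protocol 1.2 cites 83.3% with an AE in the pivotal RMS studies. If that held here, and relapse AEs were independent of other AEs with one per patient, only 16.7% of the added records would bring in a new patient. That is 7 × 0.167 = 1 to 166 × 0.167 = 28 patients, or 0.2 to 3.7 percentage points. This proportion moves much less than the event counts and the relapse row itself.

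**The case against.** The strongest defence is that 5.3.5.11 is the more specific rule and creates an exception to 5.3.5.10. But 5.3.5.10 states no such exception, and 5.2.1 refers only to 5.3.5.10. Even on that reading, AE status would still depend on admission.

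It can also be said that the by-term tables give any relapse term its own row, and that all AEs, SAEs and deaths are listed. That is correct, and it limits the harm to overview totals and to whether the row is complete. It does not make recording consistent across sites. The eCRF, which is not available here, may flag relapses, but the SAP states no rule for using such a flag.

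Several stronger readings are tempting, and the documents do not support them.

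- **A reader might infer that SAE rates follow admission habits.** 5.3.5.11 expressly keeps admissions for standard steroid treatment out of the SAE count. Only relapses admitted for another reason, or meeting another criterion in Protocol 5.2.2, can move it. Setting the record counts above against the 6.9% SAE proportion in Protocol 1.2 would therefore mislead.
- **A reader might infer that serious relapses can never reach the AE form.** 5.3.5.10 sends uncertain events there, and 5.3.5.8 requires deaths from RRMS progression to be recorded there. The SAP's SAE wording can be read as covering whatever legitimately arrives.
- **A reader might infer that admission makes a relapse Grade 3.** Protocol Table 3 describes Grade 3 as "Severe or medically significant, but not immediately life-threatening; hospitalization or prolongation of hospitalization indicated", but it applies only to IRRs and to events not listed in CTCAE. The documents do not show that relapses are graded by it.
- **A reader might infer that efficacy is double-counted.** A relapse may appear in both efficacy and safety outputs, but NEDA and ARR come from the protocol-defined relapse criteria and are not inflated.
- **A reader might infer that all rates per 100 patient-years are affected.** That list contains neither total AEs nor total SAEs. Relapses could enter only through such categories as Grade 3 or above, related events, or events leading to discontinuation.

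**Conclusion.** The conflict between Protocol 5.3.5.10 and 5.3.5.11 is real. SAP 4.6.2 leaves the handling of relapse records in the AE tables undefined. The consequence is inconsistent overall and non-serious TEAE counts across sites, seen most concretely in the 5% registry table. The SAE effect is narrow and any Grade 3 or higher effect is conditional on how relapses are graded.

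The size cannot be computed from the documents. The 7 to 166 records rest on an assumed ARR, an assumed share admitted, and full follow-up of 750 patients over the treatment period. The point concerns the recording and tabulation of safety data. It does not affect the primary efficacy result.

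**What to change.** 1. Reconcile Protocol 5.3.5.10, Protocol 5.3.5.11 and the SAE definition in SAP 4.6.2 into one rule for recording a relapse, so that its AE status does not depend on the setting of treatment.
2. State in SAP 4.6.2, table by table, whether MS relapse and progression preferred terms are counted, and how they are identified on the combined form.
3. Present the overview totals for TEAEs, Grade 3 or higher AEs and SAEs both with and without those terms. For data already collected, the version without them is the one that does not depend on which section a site followed.
4. Tabulate serious and hospitalised relapses separately.
5. Keep serious relapses in the SAE totals. Removing them from the definition could hide events that meet Protocol 5.2.2.

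The cost is a protocol clarification, some SAP wording, one preferred-term filter and a few extra table rows.

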#### **5.3.5.12 Adverse Events Associated with an Overdose or Error in Drug Administration**

An overdose is the accidental or intentional use of a drug in an amount higher than the dose being studied. An overdose or incorrect administration of study treatment is not itself an adverse event, but it may result in an adverse event. All adverse events associated with an overdose or incorrect administration of study drug should be recorded on the Adverse Event eCRF. If the associated adverse event fulfills seriousness criteria, the event should be reported to the Sponsor immediately (i.e., no more than 24 hours after learning of the event; see Section 5.4.2).

Adverse events associated with an overdose of ocrelizumab in previous clinical studies include IRRs and infection.

#### **5.3.5.13 Patient-Reported Outcome Data**

Adverse event reports will not be derived from PRO data by the Sponsor, and safety analyses will not be performed using PRO data. However, if any PRO responses suggestive of a possible adverse event are identified during site review of the PRO data, the investigator will determine whether the criteria for an adverse event have been met and, if so, will report the event on the Adverse Event eCRF.

### **5.4 IMMEDIATE REPORTING REQUIREMENTS FROM INVESTIGATOR TO SPONSOR**

Certain events require immediate reporting to allow the Sponsor to take appropriate measures to address potential new risks in a clinical trial. The investigator must report

such events to the Sponsor immediately; under no circumstances should reporting take place more than 24 hours after the investigator learns of the event. The following is a list of events that the investigator must report to the Sponsor within 24 hours after learning of the event, regardless of relationship to study drug:

- Serious adverse events (see Section 5.4.2 for further details)
- Adverse events of special interest (see Section 5.4.2 for further details)
- Pregnancies (see Section 5.4.3 for further details)

The investigator must report new significant follow-up information for these events to the Sponsor immediately (i.e., no more than 24 hours after becoming aware of the information). New significant information includes the following:

- New signs or symptoms or a change in the diagnosis
- Significant new diagnostic test results
- Change in causality based on new information
- Change in the event's outcome, including recovery
- Additional narrative information on the clinical course of the event

Investigators must also comply with local requirements for reporting serious adverse events to the local health authority and IRB/EC.

#### **5.4.1 Emergency Medical Contacts**

To ensure the safety of study patients, an Emergency Medical Call Center Help Desk will access the Roche Medical Emergency List, escalate emergency medical calls, provide medical translation service (if necessary), connect the investigator with a Roche Medical Responsible (listed above and/or on the Roche Medical Emergency List), and track all calls. The Emergency Medical Call Center Help Desk will be available 24 hours per day, 7 days per week. Toll-free numbers for the Help Desk, as well as Medical Monitor and Medical Responsible contact information, will be distributed to all investigators.

#### **5.4.2 Reporting Requirements for Serious Adverse Events and Adverse Events of Special Interest**

##### **5.4.2.1 Events That Occur prior to Study Drug Initiation**

After informed consent has been obtained but prior to initiation of study drug, only serious adverse events caused by a protocol-mandated intervention should be reported. The Serious Adverse Event/Adverse Event of Special Interest Reporting Form provided to investigators should be completed and submitted to the Sponsor or its designee immediately (i.e., no more than 24 hours after learning of the event), either by faxing or by scanning and emailing the form using the fax number or email address provided to investigators.

### **5.4.2.2 Events That Occur after Study Drug Initiation**

After initiation of study drug, serious adverse events will be reported until 96 weeks after the end of the Treatment Period. Investigators should record all case details that can be gathered immediately (i.e., within 24 hours after learning of the event) on the Adverse Event eCRF and submit the report via the electronic data capture (EDC) system. A report will be generated and sent to Roche Safety Risk Management by the EDC system

In the event that the EDC system is unavailable, the Serious Adverse Event/Adverse Event of Special Interest Reporting Form provided to investigators should be completed and submitted to the Sponsor or its designee immediately (i.e., no more than 24 hours after learning of the event), either by faxing or by scanning and emailing the form using the fax number or email address provided to investigators. Once the EDC system is available, all information will need to be entered and submitted via the EDC system.

Related SAEs must be collected and reported regardless of the time elapsed from the last study drug administration, even if the study has been closed.

Instructions for reporting post-study adverse events are provided in Section 5.6.

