### **Delayed return of peripheral B cells**

Treatment with ocrelizumab leads to rapid depletion of CD19+ B cells in blood by 14 days post treatment (first time-point of assessment) as an expected pharmacologic effect. This was sustained throughout the treatment period. The longest follow up time after the last ocrelizumab infusion from Phase II Study WA21493 in 51 patients, indicates that the median time to repletion (returned to baseline/LLN whichever occurred first of B cells was 72 weeks (range 27 – 175 weeks). Patients with prolonged B-cell depletion should be monitored until their B-cells have repleted.

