### **5.3.1 Adverse Event Reporting Period**

Investigators will seek information on adverse events at each patient contact. All adverse events, whether reported by the patient or noted by study personnel, will be recorded in the patient's medical record and on the Adverse Event eCRF.

**After informed consent has been obtained but prior to initiation of study drug**, only serious adverse events caused by a protocol-mandated intervention (e.g., invasive

procedures such as biopsies, discontinuation of medications) should be reported (see Section 5.4.2 for instructions for reporting serious adverse events).

**After initiation of study drug**, all adverse events will be reported until 96 weeks after the end of the Treatment Period, but may be extended in patients whose B-cells take longer to replete.

Related SAEs must be collected and reported regardless of the time elapsed from the last study drug administration, even if the study has been closed.

Instructions for reporting adverse events that occur after the adverse event reporting period are provided in Section 5.6.

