### **5.6 POST-STUDY ADVERSE EVENTS**

The Sponsor should be notified if the investigator becomes aware of any serious and non-serious adverse event that occurs after the end of the adverse event reporting period (defined as 96 weeks after the end of the Treatment Period), if the event is believed to be related to prior study drug treatment.

The investigator should report these events directly to the Sponsor or its designee, either by faxing or by scanning and emailing the Serious Adverse Event/Adverse Event of Special Interest Reporting Form using the fax number or email address provided to investigators.

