## Appendix 2: Follow-up Schedule of Assessments

(Including Additional B-Cell Monitoring, if required)

Patients who decide to leave the study and switch to commercially marketed Ocrelizumab, either after completion of the 96 weeks Treatment Period or after early discontinuation of the 96 weeks Treatment Period, will not enter the safety Follow-up Period.

	Follow Up	Prolonged B-Cell Monitoringa
Assessment	Visits Every 24 Weeks (± 14 days) b	Visits Every 24 Weeks (± 14 days)
Routine safety laboratory tests c	X	X
Lymphocytes subtypes d	X	X
Plasma anti-JCV antibodies sample e	X	X
Vital signs	X	X
EDSS score f	X	
Potential relapses recorded	X	X
Adverse events g	X	X
BICAMS assessment h	X	X
Concomitant medication	X	X
MRI i	X	X
Telephone contact every 8 weeks j	X	X

BICAMS= Brief International Cognitive Assessment for Multiple Sclerosis; EDSS = Expanded Disability Status Scale; JCV = John Cunningham virus; MRI = Magnetic resonance imaging; MS = Multiple sclerosis

- a Patients whose B-cells have not been repleted after 96 weeks of Follow-up Period will continue with visits every 24 weeks (± 14 days) and telephone contacts every 8 weeks until B-cell repletion (Prolonged B-cell monitoring). If the patients are receiving other B-cell targeted therapies, then the Follow-up Period is only 96 weeks regardless of their B-cell count.
- b Visits will be performed at 24-week intervals following the Early Treatment Discontinuation Visit (if discontinued early) or after the end of the Treatment Period
- c Routine safety lab: hematology, chemistry and urinalysis.
- d Lymphocytes subtypes samples for CD19+ and T-cell counts (CD4+, CD8+)
- e Plasma sampling for anti-JCV antibodies will be repeated yearly. Samples will be analyzed upon request.
- f EDSS assessment needs to be performed only once, at the first follow-up visit
- g After initiation of study drug, all adverse events must be reported until 96 weeks after the end of the Treatment Period, but may be extended in patients whose B-cells take longer to replete. Related SAEs must be collected and reported regardless of the time elapsed from the last study drug administration, even if the study has been closed (see Sections [5.3.1](#) and [5.6](#)).

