- ^l Neurological examinations will be used to distinguish relapse in MS from another neurological (non-MS) disorder. Potential relapses should be recorded throughout the treatment period. Investigators will also screen patients for signs and symptoms of PML by evaluating neurological deficits localized to the cerebral cortex, such as cortical symptoms/signs, behavioral and neuropsychological alteration, retrochiasmal visual defects, hemiparesis, cerebellar symptoms/signs (e.g., gait abnormalities, limb incoordination). Patients with suspected PML should be withheld from ocrelizumab treatment until PML is ruled out by complete clinical evaluation and appropriate diagnostic testing. A patient with confirmed PML should be withdrawn from the study.
- ^m All adverse events should be reported until 96 weeks after the last dose of study drug. After this period, the investigator should report any serious and non-serious adverse events that are believed to be related to prior study drug treatment (see Sections [5.3.1](#) and [5.6](#)).
- ⁿ All patients must receive prophylactic treatment with 100 mg methylprednisolone, administered by slow IV infusion, to be completed approximately 30 minutes before the start of each ocrelizumab infusion, and an antihistaminic drug (e.g., diphenhydramine) approximately 30 – 60 minutes before each infusion of ocrelizumab.
- ^o Ocrelizumab will be administered as two 300-mg IV infusions in 250 mL 0.9% sodium chloride each on Days 1 and 15 and one 600-mg infusion in 500 mL 0.9% sodium chloride every subsequent dose (i.e., every 24 weeks) for a maximum of 72 weeks. It is anticipated that the patient will need to stay at the hospital or clinic for a full day for the infusion visits.
- ^p A structured telephone interview will be conducted by site personnel every 8 weeks (± 3 days) to identify and collect information on any changes in the patient's health status that warrant an unscheduled visit (including new or worsening neurological symptoms) and possible events or infections. No telephone contact is needed in weeks where patient is performing on-site visits (week 24, 48, 72 and 96).

- ^q If the subject discontinues treatment early, all efforts should be made to perform the Early study treatment discontinuation evaluation visit as soon as possible after discontinuation from treatment period. Otherwise, reasons for discontinuation will be captured via telephone call.

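### The protocol gives two AE/SAE reporting windows: three sections stop at a fixed 96 weeks after treatment, while four other places allow extension until B cells replete

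*Protocol*

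**What the plan says.** **Fixed limit.** Protocol 5.4.2.2, which governs SAE reporting once study drug has started, reads: "After initiation of study drug, serious adverse events will be reported until 96 weeks after the end of the Treatment Period". Its only open-ended duty covers related events: "Related SAEs must be collected and reported regardless of the time elapsed from the last study drug administration, even if the study has been closed". Section 5.6 treats the reporting period as closed at the same point, "defined as 96 weeks after the end of the Treatment Period", and afterwards asks only for events thought to be related. Section 5.1 gives the same 96 weeks for AEs and SAEs together, without an extension.

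**Extendable limit.** Section 5.3.1 gives 96 weeks for all adverse events, "but may be extended in patients whose B-cells take longer to replete". Section 3.1.4, Appendix 1 footnote m and Appendix 2 footnote g say the same. None of them states what triggers the extension or when it ends.

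**Collection.** Appendix 2 footnote a says: "Patients whose B-cells have not been repleted after 96 weeks of Follow-up Period will continue with visits every 24 weeks", with telephone contacts every 8 weeks, until repletion. The adverse events row is marked for those visits.

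**SAP copies.** SAP Appendix 2 footnote m reads: "All adverse events should be reported until 96 weeks after the last dose of study drug". SAP Appendix 3 footnote g counts at least 96 weeks from the last infusion, allows extension, and expressly includes unrelated SAEs.

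**The concern.** Patients in Prolonged B-Cell Monitoring are there because their B cells are still depleted. Delayed B-cell return and infection are both listed as identified risks in protocol 5.1.1.1. In this period the sections disagree on whether an SAE judged unrelated has to be reported.

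Two things are at stake.

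- **Causality review.** Under 5.4.2.2 and 5.6 alone, whether a late serious infection reaches the sponsor depends on the site's causality call. Table 4 lists intercurrent illness among the grounds for a not-related judgement. Section 5.7 lets the sponsor upgrade the investigator's assessment, but only for events it receives.
- **Rates.** SAP 4.6.2 divides event counts by total time in the study, and serious infections are among the rates listed. If some sites stop reporting unrelated events at 96 weeks while their patients stay under observation, the denominator grows without matching events and the rate is biased downward.

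**Working it through.** The plan states no figure to reproduce here. The check is a comparison of texts plus date arithmetic.

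**Step 1: the same event under each rule.** Take a completer in prolonged monitoring who has an SAE more than 96 weeks after the Treatment Period, judged unrelated.

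| Place | Limit | Is this event covered? |
|---|---|---|
| Protocol 5.4.2.2 | 96 weeks, fixed; later only related SAEs | No |
| Protocol 5.6 | 96 weeks, fixed; later only events believed related | No |
| Protocol 5.1 | 96 weeks, fixed | Not by the stated limit |
| Protocol 3.1.4, 5.3.1, Appendix 1 footnote m, Appendix 2 footnote g | 96 weeks, extension permitted | If the extension is applied |
| Protocol Appendix 2, AE row | To repletion | Yes |
| SAP Appendix 2 footnote m | 96 weeks from last dose, no extension | No |
| SAP Appendix 3 footnote g | At least 96 weeks from last infusion, extension permitted | If the extension is applied |

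**Step 2: where the fixed limit falls.** Protocol 3.1 puts the last dose at Week 72 and the end of treatment at Week 96.

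- Fixed limit: 96 + 96 = Week 192.
- Time since last infusion: 192 − 72 = 120 weeks.

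**Step 3: comparison with repletion.** Section 5.1.1.1 reports, for 51 Phase II patients followed from the last infusion, that the median time to repletion "of B cells was 72 weeks (range 27 – 175 weeks").

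- Longest gap for a completer: 175 − 120 = 55 weeks (study Week 72 + 175 = 247).
- The maximum exceeds 120 weeks, so at least 1 of 51 patients did: 1/51 = 2.0%.

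**Step 4: the SAP copy.** Footnote m closes at 72 + 96 = Week 168, which is 192 − 168 = 24 weeks before the protocol's fixed limit. This applies to footnote m only.

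**The case against.** The strongest reply is that no event is shown to be lost.

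- Section 5.3.1 is the section that defines the reporting period. It covers all adverse events, which includes SAEs, and it carries the extension.
- Section 5.4 requires SAEs within 24 hours regardless of relationship and sets no end date, although it refers to 5.4.2 for details.
- Section 5.3.5.8 ties deaths to the 5.3.1 period whatever their cause.
- Section 5.1 also covers the time during the study, and 3.2 ends the study at the last B-cell monitoring visit. A monitored patient is arguably not yet post-study.
- Section 5.4.2.2 does not forbid later reports. An SAE entered on the Adverse Event eCRF at a monitoring visit would generate the safety report by the usual route.

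All of this stands, and it limits the point. A reader might infer that unrelated SAEs are dropped in still-depleted patients. The documents do not support that; they support only that the rules conflict and that the extension is optional. A reader might also infer that the SAP as a whole closes reporting at Week 168. It does not, because Appendix 3 footnote g allows extension and names unrelated SAEs. SAP section 4 lets the SAP's analyses supersede the protocol's, not its reporting rules, so these footnotes are best read as outdated copies.

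The effect on reported rates is also unproven. SAP 2.4 plans an addendum of selected analyses, with listings only where fewer than 50 patients have data.

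What the reply does not remove is that 5.4.2.2 and 5.6, read exactly, stop where 5.3.1 and Appendix 2 may continue.

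**Conclusion.** The contradiction is real and stands in the current text. Sections 5.1, 5.4.2.2 and 5.6 set a fixed limit, four other places make it extendable, and the visit schedule collects adverse events to repletion. Sites can comply and still differ on unrelated SAEs after Week 192.

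For completers the gap can last up to 55 weeks. That is set by the single longest of 51 Phase II patients, and it assumes the last infusion at Week 72 and repletion times like those in Phase II. For early discontinuers, follow-up runs from the Early Treatment Discontinuation Visit, so the limit may come sooner after the last infusion.

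The number of patients affected cannot be derived. It is tempting to fit a log-normal to the median and range (SD of the log 0.39 to 0.44, about 10% to 12% beyond 120 weeks) and multiply by a guessed number entering follow-up. The distribution is an assumption and the documents give no such number. Patients going to the extension study or to commercial drug do not enter the safety follow-up, and those on other B-cell targeted therapy stop at 96 weeks. The number is probably small. The point is worth correcting because the conflict concerns serious events in the patients depleted longest, and the correction is cheap.

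**What to change.** 1. Reconcile protocol 3.1.4, 5.1, 5.3.1, 5.4.2.2, 5.6, Appendix 1 footnote m and Appendix 2 footnote g to one AE and SAE reporting window. Match it to the collection Appendix 2 already schedules: to the end of Prolonged B-Cell Monitoring for patients who enter it, stated as a requirement and not an option.
2. In 5.6, start the post-study period from that same end.
3. For early discontinuers, state the window from the Early Treatment Discontinuation Visit.
4. Replace the outdated footnotes in SAP Appendices 2 and 3 with the reconciled text.

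The cost is wording in seven protocol places and the SAP copies, plus a few more SAE reports. No visits or calls are added, because the 24-week visits, 8-week calls and adverse event assessments already run in this period.
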